3.3 Secondary Study Endpoints

1. Montgomery-Åsberg Depression Rating Scale (MADRS) (Montgomery & Asberg, 1979) score of $\geq 50\%$. The MADRS has been used in most previous ketamine studies in adults and is designed to be sensitive to change. Although it has not been validated in adolescents, it has been used in several previous treatment studies of adolescent depression (Berard et al., 2006; von Knorring et al., 2006).
2. The Clinician-Administered Dissociative States Scale (CADSS) (Bremner et al., 1998)
3. The Profile of Mood States-Adolescent Version (POMS-A) (Terry et al., 1999)
4. The Beck Depression Inventory-II (Beck, 1988) which has been validated for adolescents (Osman et al., 2004)
5. The four-item positive symptom subscale of the Brief Psychiatric Rating Scale (BPRS) (Overall, 1962) consisting of suspiciousness, hallucinations, unusual thought content, and conceptual disorganization.
6. Relapse will be defined as a CDRS score $\geq 50\%$ of the pre-ketamine baseline. The onset of relapse will be calculated as the day halfway between the date of relapse and the previous date of response.
7. Biological endpoints will include MRI-based measures and blood-based measures of neuroplasticity.
8. The Clinical Global Impressions Scale (CGI) (Guy, 1976)
9. The Dot Pattern Expectancy task (2017) The DPX-task is a neurocognitive task that measures an aspect of goal representation known as context processing using pairs of simple dot patterns. In this task, there are four types of trials, and we refer to the trial type using letters: A means valid target, B means invalid target; X means valid cue, Y means invalid cue. Most of the trials are "target trials" (AX); in these types of trials a valid cue (A versus B) is followed by a valid probe (X versus Y). The 3 other trial types are "Non-target trials" in which either a valid cue is followed by an invalid probe (AY) or an invalid cue is followed by either a valid probe (BX) or invalid probe (BY). Participants are required to make one response for target trials, and another response for non-target trials. The nature of the cue (valid or invalid) provides the "context" for responding on a given trial. The intent of having the majority of trials as "target trials" (AX) is to encourage participants to "expect" a valid probe to follow a valid cue. A consequence of this manipulation is that participants develop a prepotency to respond with "target" responses on trials for which valid cues are presented, regardless of whether the trials were of the target (AX) or non-target (AY) type. Non-target cues provide the context that a non-target response will be required, regardless of the nature of the probe (valid or invalid). The expectancy manipulation is designed to increase AY error rates. On BX trials, participants with normal context processing must maintain the cue in order to inhibit the prepotency to respond to valid probes with a target response. Compared with controls, persons with impaired context processing may be expected to make more BX errors, whereas the AY condition is more difficult for people with intact context processing. (Jones, Sponheim & MacDonald 2010; MacDonald, III, Carter, Flory, Ferrel & Manuch, 2007; MacDonald et al, 2005).

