3.2 Primary Study Endpoints

The primary outcome measure is response status as defined by Children's Depression Rating Scale (CDRS) (Poznanski, 1985) Responders will be defined as having a significant reduction in their CDRS score ($\geq 50\%$) whereas non-responders will be defined as subjects whose scores do not show such a significant reduction or whose score increase. The percent change will be calculated by the formula below (Tao, 2009):

$$(\text{Baseline CDRS} - \text{Exit CDRS}) / (\text{Baseline CDRS} - 17)$$

Baseline CDRS: CDRS score obtained on Visit 1 – Baseline Assessment (Section 6.1)
Exit CDRS: the latest CDRS score obtained on Visit 10 - Clinical Assessment (Section 6.6) or Visit 11-16 – Follow-up Period (Section 6.7)

CONFIDENTIAL

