4.1 Inclusion Criteria

Patients will be eligible to participate in the study if all of the following conditions exist:

- 1) Willing and able to provide informed consent and assent.
- 2) Male and female adolescents aged 12 to 18 years.
- 3) Presence of recurrent MDD confirmed by the K-SADS-PL (Kaufman et al., 1997).
- 4) Current depression severity measured by the Children's Depression Rating Scale (CDRS) (Poznanski, 1985) raw score greater than or equal to 36 at screening and the day ketamine is due to be received for the first time.
- 5) Current depressive episode resistant to treatment, defined as failure to achieve remission (elimination of symptoms and restoration of pre-morbid psychosocial functioning) from at least 2 antidepressant trials. Systematic evaluation of previous antidepressant trials will be assessed by using the Antidepressant Treatment History Form (Sackeim, 2001).
- 6) If present, current antidepressant medication treatment must be dose stable for at least 2 months prior to beginning the study*
- 7) Participants should have a medical history and physical examination in the 30 days prior to initiating the ketamine infusions.

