4.4 Early Withdrawal of Subjects

When and How to Withdraw Subjects

A subject may be withdrawn from the study prior to expected completion for the following reasons:

- Participant experiences adverse side effects to the ketamine treatments that are intolerable to the adolescent or the parent.
- Participant fails to adhere to protocol requirements
- Participant or participant's parent(s) withdraw consent

If a subject exits the study for any reason (withdrawal, non-response, or relapse), he or she will continue his or her pre-study regimens and consult with his or her psychiatrist about the next step in treatment.

Data Collection and Follow-up for Withdrawn Subjects

For all participants, we will request permission during the consent process to collect naturalistic follow-up data through in person visit to clinic or video conference 6 months after the 6-week study period.

The naturalistic follow-up encounter will be as follows:

We will ask permission to contact the family to inquire about the participant. Subjects will be determined lost to follow-up if they do not respond to 4 e-mails to the primary e-mail address of parent(s) or 4 phone calls to their primary number or to their next-of-kin, or to a certified letter.

During the follow up in person visit to clinic or video conference subject will be asked to provide:

- a) A narrative interval history including following elements
 - a. Changes in medications and their effects
 - b. Therapies or other treatments they have undergone and their effects
 - c. Evolution of their symptoms during the interval
 - d. Any hospitalizations including cause and outcome
 - e. Any suicide attempts including precipitating factor (if any) and outcome
- b) Participate in a clinical interview in order for clinician to complete an assessment using CDRS-R, CADSS, CGI, and MADRS.
- c) Complete the BDI-II, Profile of Mood States – Adolescent, SHAPS and TEPS

5 Study Drug

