6.7 Visits 11-16 – Follow-up period

All participants will be asked to speak with the research team for weekly follow-up visits for 6 weeks. Participants will continue to take medications as prescribed by their doctor. At each of these visits, participants will be asked about any medication changes and will complete the same assessments as administered in visit 10 (MADRS, CADSS, POMS-A, SHAPS, TEPS, BDI-II, CGI, CDRS and BPRS).

All participants will be asked to participate in the 6 weekly follow-up visits, regardless of response.

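### Response uses a floor-corrected CDRS scale and relapse the raw scale, so one score can count as both; if both rules use the Visit 1 baseline, nine integer scores do

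*Combined protocol and SAP*

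**What the plan says.** Section 3.2 makes response a reduction of at least 50%, computed as (Baseline − Exit)/(Baseline − 17). The baseline is named: "Baseline CDRS: CDRS score obtained on Visit 1". The Exit score is "the latest CDRS score obtained on Visit 10" or at the follow-up Visits 11 to 16.

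Section 3.3 item 6 defines relapse differently: "Relapse will be defined as a CDRS score $\geq 50\%$ of the pre-ketamine baseline". It subtracts no floor and does not say which visit supplies that baseline. It dates onset as "the day halfway between the date of relapse and the previous date of response", so it relies on response being known at individual visits.

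Section 4.1 item 4 requires a CDRS "raw score greater than or equal to 36 at screening" and again on the day of the first infusion. Section 6.1 schedules a CDRS-R at Visit 1; Section 6.3 lists none among the first-infusion assessments.

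Section 7.3 asks for a time to relapse for each participant, and the Study Summary promises a group average. Neither gives a time origin or a rule for participants who never relapse.

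**The concern.** Response and relapse should be complementary: a participant gains response, then may lose it. Here one rule removes the 17-point floor and the other does not, so the score that counts as relapse is lower than the score at which response is lost. A participant can meet both definitions at the same assessment, and the protocol gives no precedence rule and does not say that relapse requires loss of response.

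Durability is the first secondary objective in Section 2 and has its own hypothesis. Its endpoint is time to relapse. An analyst who codes item 6 literally can date relapse while the participant is still well inside the response range. One who notices the clash must choose a rule, and a choice made after the data are seen would be post hoc.

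**Working it through.** The plan states no figure for this point, so there is none to reproduce. The check solves the two definitions and counts the integer scores that satisfy both.

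**Inputs.** B = Visit 1 CDRS (Section 3.2); R = baseline used for relapse (unnamed in Section 3.3 item 6); X = a post-treatment CDRS; minimum B = 36 (Section 4.1). The floor of 17 comes from the Section 3.2 formula.

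**Thresholds.**
- Response: (B − X)/(B − 17) ≥ 0.5, so X ≤ (B + 17)/2.
- Relapse: X ≥ R/2.

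**Case 1: R = B (Visit 1 in both rules).** The gap is (B + 17)/2 − B/2 = 17/2 = 8.5 points. For even B the shared integers run from B/2 to B/2 + 8, which is nine. For odd B they run from (B + 1)/2 to (B + 17)/2, also nine. Enumeration of every integer B from 36 to 113 gives nine each time. To stay clear of the relapse label, X must be below B/2, which means improvement above (B/2)/(B − 17).

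| B | Scores meeting both rules | Share of responder scores (17 upward) | Improvement needed to avoid relapse |
|---|---|---|---|
| 36 (entry minimum) | 18–26 | 9 of 10 | more than 18/19 = 94.7% |
| 50 | 25–33 | 9 of 17 | more than 25/33 = 75.8% |
| 60 | 30–38 | 9 of 22 | more than 30/43 = 69.8% |

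**Case 2: R = a first-infusion-day CDRS.** With B = 60, response needs X ≤ 38.5. The shared integers number 14 at R = 50, 11 at R = 55, 6 at R = 65, 4 at R = 70 and 0 at R = 77. In general the two ranges stop meeting once R exceeds B + 17; with B even, no integer is left at R = B + 17 either.

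**Illustration (hypothetical scores).** B = R = 50: response is X ≤ 33.5 and relapse is X ≥ 25. Follow-up week k is assumed to fall exactly on day 7k after the last infusion.

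| Visit | Day | CDRS | Improvement (50 − X)/33 | Response | Meets relapse line |
|---|---|---|---|---|---|
| 10 | within week 1 | 24 | 78.8% | yes | no |
| 11 | 7 | 24 | 78.8% | yes | no |
| 12 | 14 | 26 | 72.7% | yes | yes |
| 13 | 21 | 30 | 60.6% | yes | yes |
| 14 | 28 | 36 | 42.4% | no | yes |
| 15 | 35 | 40 | 30.3% | no | yes |
| 16 | 42 | 42 | 24.2% | no | yes |

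As written, relapse is called at Visit 12 and onset is (7 + 14)/2 = day 10.5. At loss of response, onset is (21 + 28)/2 = day 24.5. The difference is 14 days.

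**Check of the remedy.** With relapse on the floor-corrected scale but still inclusive, X ≥ (B + 17)/2, the overlap falls to 0 for even B and 1 for odd B. A strict inequality removes that last shared score.

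**The case against.** The strongest objection is that item 6 may not mean the Visit 1 score. This stands as a limit: the count of nine is conditional on Visit 1. It does not rescue the text, because an infusion-day score would have to be about 17 or more points higher before the overlap disappeared, and a lower one widens it. The unnamed baseline is a defect in itself.

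It can also be said that response is defined only for the Exit score. But item 6 needs a previous date of response, and a single Exit score can satisfy both rules anyway. A floor-corrected relapse may have been intended, but no section says so.

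Three stronger readings are tempting, and the documents do not support them.

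- A reader might infer that the two rules nearly always disagree. They do not. At B = 50, constant scores of 20 give response and no relapse under either rule. Scores of 30 then 36 give the same onset under both if relapse requires an earlier response.
- A reader might infer that relapse can never be dated later than loss of response. That holds only with a shared Visit 1 baseline. With Visit 1 = 60 and an infusion-day score of 80, response is lost at 39 but relapse starts at 40.
- A reader might infer that the primary outcome is affected, because Section 4.4 says "If a subject exits the study for any reason (withdrawal, non-response, or relapse" and early exit would change the last or lowest CDRS. That sentence describes care after an exit. The list of withdrawal reasons in the same section does not include relapse, and Section 6.7 states: "All participants will be asked to participate in the 6 weekly follow-up visits, regardless of response".

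**Conclusion.** The definitions of response and relapse are inconsistent as written. With the Visit 1 baseline in both, the relapse line is 8.5 points too low to complement the response line, and nine integer scores are both response and relapse at every eligible baseline. This follows from the two formulas alone. That it can misdate relapse is shown by the illustration, whose 14-day difference rests on hypothetical scores and exact weekly visits.

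The effect on the group average cannot be determined from the documents: it depends on the participants' courses, and no rule covers those who never relapse. Some such participants are plausible, since Section 1.4 reports 50% of the adult series not relapsed at 4 weeks, although it does not give that series' relapse definition.

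The damage is to the secondary durability endpoint. The primary paired t test compares the lowest post-treatment score with baseline and does not use relapse. The point should be fixed before analysis, but it does not undermine the primary result.

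**What to change.** Before analysis, amend Sections 3.2, 3.3 item 6 and 7.3 as follows.

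1. Name one baseline visit for both rules. If Visit 1 is kept, say how the infusion-day score required by Section 4.1 relates to it.
2. Define visit-level response at Visits 10 to 16 with the Section 3.2 formula.
3. Put the analysis definition of relapse on the same scale with a strict inequality: for example, the first visit after a response with CDRS above (Baseline + 17)/2. A stated higher line would serve if a one-point crossing (33 to 34 at a baseline of 50) should not count.
4. Date onset halfway between the last response visit and the relapse visit.
5. State the time origin, and treat responders who never relapse as censored at their last CDRS visit, since a simple average is undefined for them. Kaplan-Meier is one reasonable summary.

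Sections 4.4 and 6.7 should also be reconciled on whether relapse ends participation. No position is taken here on which should stand.

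The cost is a few lines of text and matching analysis code. CDRS is already scheduled at Visits 10 to 16, so no new data are needed. The downside is that fewer relapses may be counted.

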3.1 General Design

This is a single-group (n=20) open-label pilot study of 6 doses of IV ketamine, 3 doses per week over a 2-week period, followed by a 4-week post-treatment observational period. Symptom levels will be assessed prior to infusion, directly after infusion, 1 and 2 hours after infusion. We will also assess symptoms weekly for 6 weeks after the last ketamine infusion. A study goal is to identify neurobiological biomarkers of treatment response using neuroimaging and blood studies.

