7.3 Statistical Methods

In the following analyses, primary outcome measures will include the “per protocol” population. The secondary measures will include the “intent to treat” population.

Primary analysis: Paired t tests will be conducted between the lowest score from the post-treatment assessments and the baseline symptom levels to assess the maximum effect of ketamine infusion on symptoms for each person.

Secondary Analyses:

1. We will calculate the time to relapse for each participant.
2. Biological Mechanisms:
 - a. Neuroimaging data: Paired t tests will be conducted to evaluate pre- and post ketamine treatment changes in measures of brain functional activation, connectivity, white matter microstructure and brain metabolite concentrations. These preliminary data will be used to identify responsive measures and estimate sample sizes that would be needed to use these measures as endpoints in future studies.
 - b. Bimolecular studies to examine mechanisms of cellular resilience (insulin challenge, cytokine testing, gene expression) will be conducted to evaluate change in these pathways before and after ketamine. Analyses will be conducted by [name] at Mayo Clinic. Peripheral blood mononuclear cells (PBMCs) will be isolated from whole blood and divided into two groups. The first group will not receive any treatment. RNA will be extracted and whole genome microarray will be performed using illumina's genome-wide gene expression arrays. Differential pre- versus post-ketamine mRNA levels will be quantified and bioinformatics pathway analysis will be used to identify key differences in molecular responses to ketamine. A second subset of PBMCs will be cultured and cryopreserved. Once all samples are collected cells will be immortalized to ensure sufficient tissue availability. The following two separate analyses will then be performed:

CONFIDENTIAL

- i. Group 1 PBMCs will be stimulated with insulin and intracellular Akt, mTOR, and GSK3 gene and protein levels will be quantified following 0, 5, 15, and 30 minutes of stimulation. This signaling pathway is implicated in mediating the antidepressant response to ketamine. Western blot and rtPCR techniques will be used to quantify protein and gene expression, respectively;

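### Relapse rests on one unconfirmed weekly CDRS with no margin from the response cut-off, so even after the two scales are aligned, rating noise can label some stable responders as relapsed

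*Combined protocol and SAP*

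**What the plan says.** Section 3.2 defines response by the CDRS: "Responders will be defined as having a significant reduction in their CDRS score", with the threshold set at 50% or more. The percent change is the fall from baseline divided by baseline minus 17, so the scale's 17-point floor is removed.

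Section 3.3 item 6 defines relapse: "Relapse will be defined as a CDRS score $\geq 50\%$ of the pre-ketamine baseline". No floor is removed there. Relapse is dated as follows: "The onset of relapse will be calculated as the day halfway between the date of relapse and the previous date of response". Neither 3.3 nor 7.3 asks for a second rating, a minimum duration or a minimum worsening.

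Section 6.7 sets the number of looks: "All participants will be asked to participate in the 6 weekly follow-up visits, regardless of response". The weekly battery ("MADRS, CADSS, POMS-A, SHAPS, TEPS, BDI-II, CGI, CDRS and BPRS") includes the CDRS. Section 7.3 then says: "We will calculate the time to relapse for each participant". The Study Summary adds that an average relapse time for the group will be reported.

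Two statements bear on whether a confirming rating would exist. Section 4.4 lists relapse among the reasons for leaving the study, while 6.7 follows everyone. Section 3.1 describes treatment "followed by a 4-week post-treatment observational period", but later in the same paragraph, and in sections 2, 5.5, 6.7 and 6.8, the period is six weeks.

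**The concern.** A participant enters the at-risk group by scoring at or below one cut-off, and leaves it the first time a single later score reaches a cut-off that is no higher. Someone whose condition is steady but who sits near the line has six chances to cross it through rating variation. Each such crossing enters the analysis as a real relapse with an early date. The result also depends on how often people are rated, which is a property of the schedule and not of the treatment.

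Durability is the first secondary objective, and its hypothesis is that adolescents hold their response longer than adults have. With 20 participants, and only responders at risk, a few false early crossings move the average relapse time. The error runs against the hypothesis.

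**Working it through.** **The plan's own figure.** The documents give no relapse misclassification rate, CDRS noise SD, reliability or expected improvement, so there is nothing to reproduce. The noise and improvement inputs below are assumptions.

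**Step 1: the two cut-offs.** With baseline B and later score X, response requires (B − X)/(B − 17) ≥ 0.50, that is X ≤ (B + 17)/2 = 0.5B + 8.5. Relapse as written is X ≥ 0.5B.

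| Baseline | Response at or below | Relapse as written, at or above | Gap |
|---|---|---|---|
| 36 (entry minimum) | 26.5 | 18 | 8.5 |
| 55 | 36 | 27.5 | 8.5 |
| 65 | 41 | 32.5 | 8.5 |

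As written, the two states overlap by 8.5 points at every baseline. At B = 55 a responder must improve by more than (55 − 27.5)/(55 − 17) = 72% to avoid also meeting the relapse rule. If relapse is read on the floor-corrected scale, the cut-offs coincide. On neither reading is there a margin.

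**Step 2: six looks, simple case.** Suppose the true score lies a constant 5 points below the relapse cut-off, with independent normal error. The chance of crossing at one visit is p = 1 − Φ(5/SD), and over six visits it is 1 − (1 − p)^6.

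| SD | p | Six visits |
|---|---|---|
| 2 | 0.006 | 4% |
| 3 | 0.048 | 25% |
| 4 | 0.106 | 49% |
| 5 | 0.159 | 65% |

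At SD 4, four visits give 36%. Requiring two consecutive crossings among six gives 5%.

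**Step 3: simulation with the cut-offs aligned.** Both cut-offs are (B + 17)/2. Baseline is normal with mean 50 (SD 8) or 60 (SD 10), floored at 36. True floor-corrected improvement is normal with mean 65%, 70% or 80% (SD 15, 12 and 10 percentage points). The true level is constant, scores are integers with floor 17, and errors are independent. The denominator is participants in response at Visit 10, both truly and as rated; the six later visits are then examined (400,000 simulated participants per setting).

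| Setting | One rating | Two consecutive |
|---|---|---|
| 70% improvement, SD 4, baseline 60 | 21% | 4% |
| 70% improvement, SD 4, baseline 50 | 30% | 6% |
| All settings, SD 3 to 5 | 3% to 46% | 0.3% to 12% |
| All settings, SD 2 | 1% to 15% | 0.1% to 3% |
| Central settings, lag-1 error correlation 0.5 | 17% to 24% | 6% to 9% |
| Central settings, four looks | 16% to 24% | 3% to 4% |

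**Step 4: the rule as written.** With the raw 0.5B cut-off and SD 3 to 5, the single-rating figure is 50% to 93%. At SD 4, 20% to 69% of these stable responders have a true score at or above 0.5B, so they meet relapse with no noise at all. Two consecutive ratings then still call 55% (baseline 60) or 72% (baseline 50) relapsed at 70% improvement and SD 4.

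**Step 5: cost of confirmation.** Take aligned cut-offs, about half of responders truly relapsing (section 1.4 reports 50% of the adult patients not relapsed at four weeks), and onset spread evenly over the six visits. The single-rating rule shortens mean relapse-free time by about 0.3 to 0.8 weeks, and confirmation leaves it almost unbiased. Confirmation misses about 17% to 20% of true relapses. Most of this is structural: 1/6 = 17% begin at the last visit and have no later rating. If true relapse is only partial (back to 40% improvement), the share missed rises to about 30%.

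**The case against.** The strongest objection is that the size of the effect is assumed. The documents supply no CDRS noise SD, and for deep responders with small noise the false-relapse share falls to about 1%. Errors between visits may also be correlated, which shrinks both the problem and the benefit of confirmation. This stands, and it is why a range is given. It does not remove the point: at the central settings with correlation 0.5, the figures are still 17% to 24% for one rating against 6% to 9% for two.

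A second objection is that confirmation trades one error for another. It misses late relapses and so can lengthen apparent durability, in the direction of the hypothesis. This also stands, and it means that confirmation should not replace the single-rating version.

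A third is that a confirming rating may not exist, given section 4.4 on exit at relapse and the 4-week statement in 3.1. That is a reason to reconcile those passages before relying on the fix.

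A reader might also infer that 50% to 93% of stable responders would be mislabelled by rating noise under the rule as written. The documents do not support that reading: those figures mainly reflect the 8.5-point overlap between the two cut-offs, which is a separate problem and which confirmation alone does not cure.

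**Conclusion.** The point holds in a limited form. Relapse is called on one weekly CDRS, with no margin from response and no confirmation over six looks. Once relapse is on the response scale, noise can still mislabel about 1% to 46% of stable responders, with 21% to 30% at SD 4 and 70% improvement. These figures rest on the assumed noise SD, the assumed improvement and independent errors.

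It would go too far to infer that the trial's efficacy result is at risk. This is a secondary, exploratory durability endpoint in a 20-person open-label pilot, and the primary paired t test does not use relapse. Nor can a particular false-relapse rate be attributed to this trial, because the documents do not give the inputs.

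**What to change.** 1. In 3.3 item 6, put the relapse cut-off on the floor-corrected scale of 3.2. Without this step, confirmation leaves most of the error in place.
2. For analysis only, define relapse as that criterion met at two consecutive weekly ratings. Apply the existing halfway-day rule to the first of the two, and state how a missed visit between them is handled.
3. In 7.3, report the single-rating version beside it. Show a crossing at a participant's last rating as unconfirmed and count it in a sensitivity analysis. Read durability from both versions.
4. Reconcile 4.4 (relapse as a reason for exit) with 6.7 (everyone followed), and the 4-week with the 6-week period in 3.1, so that it is clear whether a confirming rating will exist.

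The cost is a few sentences in 3.3 and 7.3. No new assessment is needed as long as the weekly visits continue for everyone, and this analysis definition does not alter care. The downside is the missed true relapses, mainly late ones, which is why both versions are needed.
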